Given the critical and urgent need to improve models of care for pediatric TB that include strengthened case finding and use of innovative diagnostics and drugs that may offer improved outcomes for children with TB infection or disease, The Elizabeth Glaser Pediatric AIDS Foundation (EGPAF) is implementing the Unitaid-funded Catalyzing Pediatric TB Innovation (CaP TB) project. CaP TB will develop and implement innovative models of care and accelerate the broad introduction of WHO-recommended and quality-assured drugs and diagnostics that will help bring care closer to children living with and at risk for TB and close the pediatric TB gap.

This protocol describes the program evaluation that will help to document the outcomes of the CaP TB project.

II. Project Goals and Objectives

A. Goal

To evaluate the effectiveness of the CaP TB project across ten countries on key service delivery and clinical outcomes and compare these outcomes to those obtained at baseline.

B. Objectives

1. Primary Objective

1. To evaluate the below TB service indicators and clinical outcomes for children 0-14 in facilities implementing the CaP TB project:
2. To evaluate the below TB service indicators and clinical outcomes for children 0-14 in facilities implementing the CaP TB project:
 - a. Number and proportion of children screened for TB among clinic attendees
 - b. Number and proportion of presumptive TB cases identified among children screened for TB
 - c. Number and proportion of presumptive TB cases referred for lab-based TB diagnosis
 - d. Number and proportion of pediatric presumptive TB cases who are tested with Xpert
 - e. Number and proportion of pediatric TB cases diagnosed with active TB among presumptive pediatric TB cases.
 - f. Number and proportion of presumptive TB cases identified among children screened for TB
 - g. Time between when a child is identified as a presumptive TB case and when the child is diagnosed with TB
 - h. Number and proportion of pediatric TB cases started on DS-TB treatment
 - i. Time between when a child is identified as a presumptive TB case and when the child is initiated on TB treatment
 - j. Number and proportion of pediatric DS-TB cases or cases treated with first-line TB treatment who achieve treatment success
 - k. Number and proportion of all TB index cases for whom successful contact tracing has been done
 - l. Number and proportion of pediatric household contacts who are negative to TB screening

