 - GeneXpert diagnostic assays (i.e Xpert MTB/RIF Ultra)^{xxxii}
 - Quality-assured pediatric dispersible formulations of fixed dose isoniazid-rifampicin-pyrazinamide and rifampicin-isoniazid as well as ethambutol single formulation for the treatment of active TB disease;

- Quality-assured pediatric formulations of dispersible isoniazid single formulation and fixed dose rifampicin-isoniazid for preventive therapy^{XXXIII}.
- Supporting the introduction and use of e-/m-health technologies (i.e connectivity solutions, SMS-reminders) to strengthen performance of TB screening at household level, linkage to care and/or patient's treatment adherence strategies

Drugs and diagnostics used in CaP TB must have approval from a stringent regulatory agency or be recommended by the Global Fund ERP, the WHO prequalification program or WHO Global TB program and be registered by the country national regulatory authority or have an exemption for import and routine use in the country. Cepheid recommends that gastric aspirate (GA) samples tested on the Cepheid GeneXpert platform be centrifuged to improve yield. As some of our Xpert testing sites will not have access to the appropriate centrifuge and infection control equipment, we will use direct GA specimens without centrifugation for Xpert testing. Testing without a concentration step (achieved through centrifugation) may reduce the sensitivity of Xpert testing for this specific sample type. It will not affect specificity. As the sensitivity of GA even with a centrifugation step is estimated to be 83% according to a WHO meta-analysis, WHO guidelines^{XXXIV} recommend that a negative result from a GA sample tested on Xpert not be used to definitively rule out TB. As the sensitivity from testing without a centrifugation step may be lower, we will stress in our trainings that a negative result from an Xpert test on GA does not rule out TB. This practice will be reviewed with the National TB Program before implementation.

3. Duration of the Project

Data collection of pre-intervention retrospective baseline data collection will take place in the months prior to or immediately after the start of CaP TB project interventions. Post-intervention data collection will take place once the facility is enrolled in CaP TB and will be on-going over the course of the project (through September 30, 2021). It is expected that most countries will begin enrolling pilot facilities by September 2018.

V. Description of Project Evaluation

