The CaP TB model represents one potential way of improving the care of pediatric TB. However, it will be important to measure this model's effect on key service and clinical indicators related to pediatric TB in order to help guide future programming and resource prioritization. In order to describe the effect of the CaP TB model on these indicators, we plan a pre- and post-intervention evaluation in all project countries. We have chosen this pragmatic approach to allow us to compare the outcomes after we begin CaP TB implementation with the same indicators baseline (pre-implementation). This can help us define the effect of our specific project on the project evaluation indicators. As this is an evaluation of program implementation a randomized approach would not be feasible for both programmatic and financial reasons. We do recognize that secular trends may affect our outcomes, but we feel that the duration of the evaluation (over several years) and the large size and multi-country nature will help to mitigate that risk.

A. Pre-intervention Evaluation- Baseline assessment

In each country, a pre-intervention retrospective data collection will take place in a sub-set of project sites.

This data collection activity will:

1. Capture data that will answer the TB service indicators and clinical outcomes listed in the primary objectives.
2. Capture key data points that will be needed to estimate project targets

The main objectives of the CaP TB interventions are:

- to increase the number of children diagnosed with TB
- To increase the number of children who are started on and complete DS-TB treatment
- To increase the number of children who are started on and complete TB preventive therapy.

Key indicators that will be used to monitor project interventions and assess impact will therefore be:

- Number of pediatric cases diagnosed with active TB disease
- Number and proportion of pediatric DS-TB cases who achieve treatment success
- Number and proportion of pediatric patients started on preventive therapy of those who are eligible for preventive therapy
- Number and proportion of pediatric patients on preventive treatment who completed therapy

Data sources for these indicators during the pre-intervention phase are described in Table 1.

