Project data sample size: As this is a project evaluation, no specific sample size has been calculated. However, we estimate that the project will increase case detection by 2-fold and result in an additional 16,471 pediatric TB cases being treated.^{xxxix} This is based on an assessment of the number of children we project to screen (both HIV positive and HIV negative) in our project sites throughout the project. From the literature, we estimate that approximate Number Needed to Screen (NNS) to identify 1 TB case is 41 children. Assume that Number Needed to Screen (NNS) to identify 1 TB case is 41 (estimated NNS when symptom based screening is the only primary screening done)^{xl, xli}. Preventive treatment coverage is estimated to increase by four-fold, with an additional 52,317 children to be initiated on preventive therapy. This is based on the estimated number of child TB contacts we will identify through contact tracing plus HIV-infected children who qualify for preventative treatment.

To compare pre- and post-intervention outcomes, we will use either the ratio of the two proportions (relative risk) or the difference between the two proportions (risk difference). We will use Z-tests to assess the statistical significance of the estimated effect of CaP TB.

For measuring turn-around-time (TAT) between when a child is identified as a presumptive TB case and when the child is diagnosed with TB and the TAT between when a child is diagnosed as a presumptive TB case and when the child initiates TB treatment, if the TATs are approximately normally distributed, we will use the paired t-test to assess for statistical significance, otherwise we will use the Wilcoxon rank sum non-parametric test.

A. Quality Assurance

All data collectors will be trained in quantitative data collection by EGPAF staff. Prior to training, all data sources, abstraction and collection tools and procedures will be reviewed and tested. The HQ EGPAF team will provide on-going support to in-country teams throughout program implementation and all data collection activities.

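### The test of time to treatment uses only children who start, so the before and after groups may be selected differently; label it as conditional and add a comparison that counts non-starters

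*Combined protocol and SAP*

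**What the plan says.** Indicator i in Section II.B.1 is "Time between when a child is identified as a presumptive TB case and when the child is initiated on TB treatment". Just before it, indicator h is "Number and proportion of pediatric TB cases started on DS-TB treatment". Secondary objective a (Section II.B.2) compares all these indicators with baseline in a subset of sites.

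Section IX analyses the two separately. For proportions such as h, it takes a ratio or difference and says "We will use Z-tests to assess the statistical significance of the estimated effect of CaP TB". One of the two turnaround times (TAT) it tests is "the TAT between when a child is diagnosed as a presumptive TB case and when the child initiates TB treatment". For these, "if the TATs are approximately normally distributed, we will use the paired t-test to assess for statistical significance", and "otherwise we will use the Wilcoxon rank sum non-parametric test". It gives no time-to-event method, no rule for a child without an initiation date, and no statement that h and i are read together.

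Section V.A lists among the main objectives "To increase the number of children who are started on and complete DS-TB treatment". Section IV.A.2 includes digital tools meant to "strengthen performance of TB screening at household level, linkage to care and/or" adherence.

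**The concern.** A child who never starts treatment has no TAT, and neither named test can use that child as planned. The restriction to starters is not written out. It follows from the outcome definition and the choice of tests.

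Starting treatment is also something the project is designed to change, so the test conditions on a possible effect of the intervention. If better linkage brings in children who would previously have been lost, and they take longer to start, they add long times to the later period that have no counterpart in the earlier one. A reader would then see longer delay where access had improved.

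A second selection works the opposite way. Post-intervention collection ends on 30 September 2021. A child identified shortly before then is counted only if treatment began quickly. The baseline window is set back in time so that six-month outcomes can be observed, and no similar set-back is stated for the later period.

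**Working it through.** The plan states no sample size, significance level, TAT distribution or initiation share for this comparison, so there is no figure to reproduce. All inputs below are assumptions that show the mechanism; none is an estimate for this project.

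**Hand example, per 100 diagnosed children.** Before: 60 start on day 5 and 40 never start. After: 60 start on day 5, 30 on day 20 and 10 never.
- Mean TAT among starters: 5 days before; (60×5 + 30×20)/90 = 10 days after.
- Rank-sum test, 60 against 90 starters: p = 6×10⁻⁷, later period slower. The median is 5 days in both periods.
- All diagnosed children: started by day 7 or 14, 60% in both periods; by day 30, 60% against 90%.

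**Simulation.** Assumed: 200 diagnosed children per period, two-sided 0.05, 1,000 replicates. Children who would start in either period have a lognormal TAT with median 7 days and log-SD 0.8, unchanged by the project. Newly retained children have the same spread around the median shown.

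| Share starting, before → after | Median TAT of newly retained | Starters' median | Rank-sum declares slower | All diagnosed, started by day 14 | All diagnosed, started by day 28 |
|---|---|---|---|---|---|
| 70% → 80% | 14 d | 7.0 → 7.6 | 13% | 56.6% → 61.6% | 67.1% → 75.2% |
| 70% → 80% | 21 d | 7.0 → 7.8 | 25% | 56.5% → 59.5% | 67.0% → 73.4% |
| 70% → 90% | 14 d | 7.0 → 8.1 | 35% | 56.4% → 66.4% | 67.0% → 83.2% |
| 70% → 90% | 21 d | 7.0 → 8.7 | 60% | 56.4% → 62.5% | 67.2% → 80.0% |
| 70% → 95% | 21 d | 7.0 → 9.1 | 80% | 56.2% → 63.9% | 66.9% → 83.0% |
| 80% → 95% | 21 d | 7.0 → 8.1 | 44% | 64.4% → 69.0% | 76.6% → 86.2% |
| 90% → 95% | 21 d | 7.0 → 7.3 | 8% | 72.5% → 74.1% | 86.3% → 89.5% |
| 70% → 90% | 7 d | 7.0 → 7.0 | 3% | 56.5% → 72.6% | 67.2% → 86.3% |

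Closed-form check of the fourth row, where a lognormal mean is median × exp(0.8²/2) = median × 1.377:
- Mean among starters before: 7 × 1.377 = 9.6 days. After: (0.70×7 + 0.20×21)/0.90 × 1.377 = 13.9 days.
- Started by day 28 before: 0.70 × Φ(ln(28/7)/0.8) = 0.70 × 0.958 = 67.1%. After: add 0.20 × Φ(ln(28/21)/0.8) = 0.20 × 0.640 = 12.8%, giving 79.9%.

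**If the project also speeds up the other children.** With 70% → 90% and retained children at 21 days, a fall from 7 to 5 days for the others is declared faster in only 7.5% of replicates. With 90% → 95%, the same speed-up is detected in 88%.

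**Can baseline registers support a comparison that counts non-starters?** Table 1 gives TB registers or logbooks as the baseline source for h, which may list only children who started. For indicators e and i it also names presumptive TB registers, where a diagnosed child who did not start could appear. Suppose, in the hand example, baseline registers omit the 40 never-starters. The day-30 comparison becomes 60/60 (100%) against 90/100 (90%). The pooled proportion is 150/160 = 0.9375, the standard error is √(0.9375 × 0.0625 × (1/60 + 1/100)) = 0.0395, z = 0.10/0.0395 = 2.53 and p = 0.01 against the project. Applied at every site, the alternative could itself give the wrong sign.

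**The case against.** The strongest reply is that indicator h sits beside indicator i and would show the change in retention: 60% to 90% in the hand example. TAT is not among the key impact indicators in Section V.A, so no main conclusion rests on it. Time among starters is also a legitimate measure of service speed when reported next to coverage. All of this stands and limits the importance of the point. It does not correct the TAT test, and the plan does not say the two results are read together.

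The size is also wholly assumed. No passage supports a slower start among newly retained children, and the one cascade study described in Section I places the largest shortfall at diagnosis. That stands too.

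A reader might infer that the planned analysis will show the project as slower. The documents do not support this: it requires both a material rise in initiation and slower retained children, and end-of-study truncation pulls the other way. A reader might also infer that h guarantees a usable baseline denominator everywhere. It does not: Section V.A says some baseline data will be missing from existing registers, and patient IDs are collected only where they exist.

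**Conclusion.** The point holds as a conditional one. As planned, the pre/post test of time to treatment compares only starters, and the project is meant to change who starts. The result can therefore mislead in either direction. An apparent slowing needs better retention together with later starts among those retained. In the assumed scenarios that meet both conditions, with other children unchanged, it was declared in 8% to 80% of replicates. With no difference in speed the distortion disappears. The documents fix neither quantity, so the size in this project cannot be stated. Because h partly mitigates and TAT is not a key impact indicator, this is a minor improvement to the analysis, not a threat to the main findings.

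**What to change.** 1. Label the TAT comparison as conditional on starting treatment. State that it is not evidence of slower or faster service unless read with indicator h. Keep median TAT as description.
2. Add a pre/post comparison of the cumulative proportion of children diagnosed with TB who had started treatment by fixed days (for example 7, 14 and 30) after presumptive identification. Count never-starters as not started, censor only at data cut-off, and use site-clustered standard errors.
3. Base that test on sites with data in both periods whose baseline presumptive or diagnostic registers record diagnosed children who did not start. Elsewhere report it descriptively, with the baseline proportion labelled an upper bound.
4. State that the comparison is conditional on diagnosis, which the project also aims to change through its expected two-fold rise in case detection.

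Cost: a few lines of analysis-plan text, one added analysis of dates already collected, and a check of which baseline registers list diagnosed non-starters. The downside is that fewer sites contribute to the added test.

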 - m. Number and proportion of screened negative pediatric contacts eligible for preventive therapy
 - n. Number and proportion of pediatric patients started on preventive therapy of those who are eligible for preventive therapy
 - o. Number and proportion of pediatric patients on preventive treatment who completed therapy

2. Secondary Objectives

- a. To determine the effect of the CaP TB project on the above TB service indicators and clinical outcomes compared to baseline (standard of care) in a subset of project sites.
- b. Utilize the evidence generated from this program evaluation to support strategic recommendations to improve pediatric TB care.

- c. Utilize clinical aggregated data generated by this study to inform cost-effectiveness analysis of pediatric TB interventions implemented by CaP TB project that can contribute informing childhood TB planning and strategic allocation of financial resources
- d. Utilize evidence generated from this program to assess the impact of measures enforced to control the COVID -19 pandemic on accessibility and availability of pediatric TB services

III. Expected Outcomes of the Study

The main expected outcome of CaP TB project is to reduce morbidity and mortality associated with pediatric TB^{xxx} by reducing the pediatric TB diagnostic and treatment gap, increasing coverage of quality assured TB treatments, as well as scale up of TB preventive therapy through innovative models of care for pediatric TB that focus on integration and decentralization. We expect that this program evaluation will document a positive impact of the CaP TB model, with estimated two-fold increase in case detection and four-fold increase in pediatric patients started on TB preventive therapy based on project target estimates. The evaluation of the CaP TB project will allow for dissemination of the results and further uptake of proven models by other countries.

IV. Study Design

We are planning a pre-/post-project (quasi experimental) intervention evaluation. The population will include all pediatric patients (0-14 years of age) who present to a CaP TB project site in any of the 10 countries and receive TB services (including screening, diagnosis and treatment for active TB, and provision of TB preventive therapy).

A. Methodology

[figure not shown]
1. Description of the CaP TB Project

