In each site, trained data collectors will retrospectively extract data from appropriate registers, logs, and in some cases patient files, for a period of 12 months starting 6 or more months before the start date of data extraction. This time frame has been selected in order to allow to accurately measure indicators on treatment completion for both drug-sensitive TB treatment and preventive therapy (treatment lasts 6 months in both cases). In certain cases, the data sampling frame will start more than 6 months before the data extraction if CaP TB interventions had started during the sampling frame. Thus the sampling frame was chosen so that the end date of retrospective pre-intervention data abstraction would be before the start of any intervention to ensure that the baseline data was not affected by the early activities. For some indicators, baseline data will not be available in existing registers or logbooks. Data collectors will extract data from all pediatric entry points within the facility, including MNCH, HIV, nutrition and other relevant pediatric health care entry points. Only required variables will be abstracted and entered into the password-protected computers. Data with the patient date of birth (DOB), patient ID (if any), TB treatment ID and preventive treatment ID will be collected. The patient ID (if any), TB treatment ID and preventive treatment ID will all be encrypted before being uploaded into the CaP TB Database Entry Tool. DOB will be abstracted in order to facilitate tracking across registers if needed, as well as for data quality assurance purposes. This information will only be used to link registers. Only de-identified patient data will be abstracted into our global project

database. No other unique identifiers such as contact details of the children or their caregiver will be abstracted from the registers. Data from included pediatric patients will be extracted from the registers and recorded in the CapTB Baseline Data Abstraction form from where the data will be entered into a CaP TB Database Entry Tool (Excel-based and/or Web/mobile App-based) developed for pre-and post-intervention data , in a password protected computer and/or Android device (See Annex A: CapTB Information System).

The target population for the pre-intervention assessment is the records of any pediatric patient (0-14 years of age) who attend one of the sub-set of pilot sites in any of the 10 CaP TB countries who receive TB services. TB services include:

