Location of activity	10-20 purposively selected pilot sites in each country, for a total of up to 200 sites across all ten countries. Sites will be selected based on geography (urban vs rural) and health facility level. We estimate that 12 months of data will be sufficient to appropriately assess the indicators from the primary objectives under standard of care conditions. The overall sample size in each country and per facility sample size will vary greatly by facility level, pediatric population density and indicator. However, we estimate that we will collect data for at least 5 children with presumptive TB in each clinic.	Up to 70 sites in each country for a total of up to 700 sites across all ten countries.
Timing	15-20 CaP TB pilot sites in each country	All CaP TB sites across 10 countries (up to 700 sites)
Method	Retrospective data collection will occur upon site selection. It is estimated that the retrospective data collection for all sample project sites in a given country will take six to ten weeks.	Data collection will begin when each site begins implementation of CaP TB and will go on through the end of the project
	Data abstraction of TB registers, HIV registers, PMTCT registers and other relevant logbooks	Data abstraction from clinic attendees registers, Pediatric TB Intensified Case Finding Screening Tool, CaP TB Pediatric TB Form, TB treatment register, TB preventive therapy register and other TB registers and logbooks as needed

Informed Consent documents	Informed consent waiver to be requested	Informed consent waiver to be requested
Data collection tool	Baseline data abstraction tool	Pediatric TB Intensified Case Finding Screening Data Abstraction Tool and CaP TB Database Entry Tool

IX. Data Management and Statistical Analysis

Quantitative de-identifiable data extracted from the source documents will be coded and entered directly into a database that will be designed specifically for the project and stored on a secure cloud server. Data will be aggregated in the database and entered into an electronic dashboard that will demonstrate the data standardized to project indicators and data elements. Frequencies will be calculated for each response and descriptive statistics will be calculated.

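### Turnaround time is assigned a paired test if normal and an unpaired test if not; no single unit of analysis fits both, and the plan names none.

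*Combined protocol and SAP*

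**What the plan says.** Section II.B.1 lists two times in the primary objective: from identification as a presumptive case to diagnosis (item g) and to the start of treatment (item i). Both are measured per child. Section II.B.2 asks for each indicator to be "compared to baseline (standard of care) in a subset of project sites".

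The only test rule for these times is in Section IX. The condition is "if the TATs are approximately normally distributed"; in that case "we will use the paired t-test to assess for statistical significance, otherwise we will use the Wilcoxon rank sum non-parametric test".

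The two periods are defined elsewhere:

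- **Baseline (Section V.A):** 12 months of records from a subset of project sites, with the window set so that "the end date of retrospective pre-intervention data abstraction would be before the start of any intervention". The section also warns: "For some indicators, baseline data will not be available in existing registers or logbooks".
- **Post-intervention (Table 3, Section VIII.A):** "Data collection will begin when each site begins implementation of CaP TB and will go on through the end of the project".
- **Volume (Table 3):** for baseline, "we estimate that we will collect data for at least 5 children with presumptive TB in each clinic".

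Section VII.A does describe a facility-level pre/post comparison limited to sites with both periods. It belongs to the cost-effectiveness analysis, and its site rates cover notifications and treatment and preventive-therapy starts, not turnaround time.

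**The concern.** Normality and pairing are separate questions. Whether observations are paired follows from the design; whether they are normal follows from the data. Here a normality check also changes the assumed design from paired to independent and, in effect, the unit of analysis from site to child. The condition is also placed on the times themselves, whereas a paired t-test needs approximate normality of the differences.

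The pre/post comparison of both turnaround times rests on this one sentence. As it stands, the analyst may face a test that cannot be run, a test that discards the pairing, or a test that ignores site. The choice of unit is left open until the data have been seen.

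**Working it through.** The plan states no sample size, alpha, SD, ICC or correlation for turnaround time, so there is no figure of its own to reproduce. The check sets each candidate unit against each test, then illustrates the consequences under stated assumptions (two-sided 5%).

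**1. Units against tests**

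| Unit | Paired t-test | Rank-sum test |
|---|---|---|
| Child | Cannot be run: the windows do not overlap, the children differ, and nothing links one to another | Can be run, but treats children at one site as independent |
| Site | Fits: the same sites appear in both periods | Treats the two periods of one site as independent; signed-rank is the paired counterpart |

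No row suits both columns.

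**2. Site level**

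Assumed: 100 sites with both periods, normal site summaries, a shift of 0.3 SD, and pre/post correlation r. The paired t-test can be checked by hand. Its noncentrality is 0.3 × √100 / √(2(1 − r)). At r = 0.5 this is 3 / √1 = 3.0, which gives 84% power; at r = 0 it is 3 / √2 = 2.12, which gives 56%. Simulation (6,000 replicates per cell):

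| r | Power: rank-sum | Power: signed-rank | Power: paired t | Rank-sum rejection under the null |
|---|---|---|---|---|
| 0 | 54% | 54% | 56% | 4.8% |
| 0.3 | 56% | 69% | 71% | 2.5% |
| 0.5 | 55% | 83% | 84% | 0.7% |
| 0.8 | 60% | over 99% | over 99% | 0.0% |

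The last column agrees with the large-sample size of an unpaired test on paired data, 2 × (1 − Φ(1.96 / √(1 − r))). This is 5.0% at r = 0, 1.9% at 0.3 and 0.6% at 0.5.

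**3. Child level**

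Rank-sum false-positive rate with no true change. Assumed: 150 sites, between-period correlation of site effects 0.5, and 3 or 6 times as many children after as before (4,000 replicates per cell):

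| Mean baseline children per site | ICC 0.05 | ICC 0.1 |
|---|---|---|
| 2 | 5–9% | 6–10% |
| 5 | 7–13% | 8–18% |
| 20 | 13–29% | 20–41% |

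The low end has equal site volumes. The high end has variable volumes (coefficient of variation 1 for the underlying site rate) that are independent between periods.

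**4. Sites lost if both periods are required**

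Time to diagnosis exists only for diagnosed children. A site at the stated floor of 5 presumptive children has no baseline value with probability (1 − p)^5, where p is the assumed share diagnosed:

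- p = 0.1: 0.9^5 = 0.59
- p = 0.2: 0.8^5 = 0.33
- p = 0.4: 0.6^5 = 0.08

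**The case against.** The strongest reply is that the child is the natural unit. The times are defined per child, and Section X speaks of patient-level data for the pre/post analysis. On that reading rank-sum suits two groups of children and *paired* is a one-word slip. Durations are often skewed, so the rank-sum branch might be the only one used. This is a fair guess at the intent, but the sentence then still prescribes a test that cannot be run, and the fallback still ignores site. The opposite guess, a slip for signed-rank at site level, is equally open.

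A second reply is that the child-level error rates come from ignored clustering, not from mixing the two tests. That is correct: changing *paired* to *two-sample* would leave those rates as they are. They show why the child-level reading is no safe harbour; they do not measure the mismatch itself.

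Third, the upper rates depend on generous assumptions. With a between-period correlation of 0.8 (ICC 0.1, ratio 3, equal or shared volumes) the rates fall to about 5–8% at 5 children and 12–18% at 20. Independent volumes are also doubtful, since Table 3 ties volume to facility level and population density. A rough scale follows from Section IX. A doubling that adds 16,471 treated cases implies about 16,471 without the project. Over 700 sites and an assumed three years, that is 16,471 / 2,100 ≈ 8 per site-year, nearer the 5-child row than the 20-child row, although pilot sites may be larger. The top of the range is therefore unlikely to be typical.

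Finally, Section XIV makes a biostatistician responsible for developing an analysis plan, which could settle the unit. No such decision appears in these documents.

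**Conclusion.** The concern holds. The rule for turnaround time is wrong as written, because no unit of analysis suits both named tests and none is stated. This conclusion follows from the text and needs none of the assumed figures.

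The consequence depends on the reading. At site level the error costs power and makes the test conservative: nothing at zero correlation, and about 28 percentage points at r = 0.5 (83 − 55). At child level the paired test is unavailable and the rank-sum p-value can be too small, by little with few children per site and substantially with many. All correlations, ICCs, volumes and site numbers behind these figures are assumptions.

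This is a should-fix. Both times are in the primary objective, but their pre/post comparison is a secondary one. Section V.A introduces its impact measures with "Key indicators that will be used to monitor project interventions and assess impact will therefore be", and turnaround time is not among the four that follow.

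**What to change.** Name the unit in Section IX before analysis and use a method that matches it, in sites with turnaround times in both periods. Either of these would do:

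- **(a) Site as unit, the smaller change.** *The unit is the site. The median turnaround time is calculated per site and period. Site differences (post minus baseline) are tested by the paired t-test if the differences are approximately normal, otherwise by the Wilcoxon signed-rank test, and the change is reported with a 95% CI.*
- **(b) Child as unit, preferable if many sites have few children.** *Log-transformed turnaround time is compared by a mixed model with fixed effects for period and country and random effects for site and site-by-period.* If a constant is added to handle same-day results, describe the resulting ratio as that of turnaround time plus the constant.

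Option (a) gives a site with one child the same weight as a site with 100, so it targets the typical site rather than the typical child. The sponsor should choose according to which is of interest.

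Under either option add: *The number of sites excluded for lack of a baseline or post-intervention turnaround time is reported.*

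The cost is one or two sentences, slightly more analysis work and no new data. The real drawback is losing sites without a value in both periods, which at the floor of 5 presumptive children could be a large share; larger sites lose less.
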